## 6.10 Costs

Patients and/or their insurance companies will be responsible for the cost of all radiation treatment visits, consultation, procedures, and SBRT treatments.

The sponsor will cover the cost of the study drug Avelumab and support for its administration. The sponsor will cover the cost of the research blood draws.

## 6.11 Compensation

None

# 7. DRUG INFORMATION

## 7.1 Avelumab

Please refer to the Product Label and Investigator's Brochure for more comprehensive information.

**Other names for the drug:** MSB0010718C

**Mechanism of action (or Product description):**

Avelumab binds PD-L1 and blocks the interaction between PD-L1 and PD-1. This removes the suppressive effects of PD-L1 on anti-tumor CD8+ T cells, resulting in the restoration of cytotoxic T cell response.

**Availability:** Clinical supplies are provided by Pfizer, and will be affixed with a clinical label in accordance with regulatory requirements.

**Dosage Forms and Strengths:**

Avelumab drug product is a sterile, clear, and colorless concentrate for solution presented at concentrations of 10 mg/mL and 20 mg/mL in European Pharmacopeia (Ph. Eur.) and United States Pharmacopeia (USP) type I glass vials closed with a rubber stopper and sealed with an aluminum Flip Off® crimp seal closure.

Each single-use 10 mg/mL vial contains 80 mg of avelumab as a preservative-free acetate-buffered solution (pH 5.5) containing Mannitol, Methionine, and Polysorbate 20 (Tween 20).

Each single-use 20 mg/mL vial contains 200 mg of avelumab as a preservative-free acetate-buffered solution (pH 5.2) containing Mannitol, and Polysorbate 20 (Tween 20).

**Preparation and Delivery:**

Avelumab will be prepared according to the product label unless otherwise directed in the Pharmacy Manual.

Avelumab drug product must be diluted with 0.45% or 0.9% saline solution (sodium

chloride injection) supplied in an infusion bag. Detailed information on infusion bags and medical devices to be used for the preparation of the dilutions and subsequent administration will be provided in the manual of preparation.

To prepare the dilutions, subsequent preparation steps must be accomplished by adequate trained personnel under a laminar flow box using aseptic techniques:

Prior to the preparation of the dilution for final infusion, allow each vial to equilibrate to room temperature. Use a disposable syringe equipped with a needle of suitable size to remove a volume of sodium chloride solution to be replaced by avelumab from the infusion bag and discard the removed solution. Use a new disposable syringe equipped with a needle of suitable size to inject a volume of avelumab drug product identical to the discarded volume of sodium chloride solution into the infusion bag. Gently invert the mixture 10 times. Infusion bags must not be shaken, in order to avoid foaming or excessive shearing of the protein solution. The preparation must be carefully inspected as it should result in a homogeneous looking clear solution, free of visible particles.

Avelumab is administered on an outpatient basis. Avelumab 10mg/kg body weight, diluted with 0.45% or 0.9% saline solution, will be administered as a 60 minute intravenous (IV) infusion every 2 weeks. No Avelumab dose reductions are permitted on this study. Specific instructions for the preparation infusion fluid and administration of infusion solution are provided in the Pharmacy Manual.

**PreMedication:**

Subjects will receive avelumab by IV infusion following pretreatment with H1 blockers and acetaminophen once every 2 weeks. Premedication with an antihistamine and with paracetamol (acetaminophen) (for example, 25-50 mg diphenhydramine and 500-650 mg paracetamol [acetaminophen] IV or oral equivalent) approximately 30 to 60 minutes prior to each dose of avelumab is mandatory. This regimen may be modified based on local treatment standards and guidelines as appropriate provided it does not include systemic corticosteroids.

**Storage and stability:**

Avelumab drug product must be stored at 2°C to 8°C until use. The storage condition is based on data from ongoing long term stability studies with avelumab.

Avelumab drug product stored at room (23°C to 27°C) or higher temperatures for extended periods of time might be subject to degradation. Avelumab drug product must not be frozen. Rough shaking of the solution must be avoided.

For application in clinical trials, avelumab drug product must be diluted with 0.45% or 0.9% saline solution (sodium chloride injection) supplied in an infusion bag. The chemical and physical in-use stability for the infusion solution of avelumab in 0.45% or 0.9% saline solution has been demonstrated for a total of 24 hours at room temperature. However, from a microbiological point of view, the diluted solution should be used immediately and is not intended to be stored unless dilution has taken place in controlled and validated aseptic conditions. If not used immediately, in-use storage times and conditions prior to

administration are the responsibility of the user.

**No other drugs should be added to the solution for infusion containing avelumab.**

**Route of administration for this study:** Intravenous infusion over 1 hour.

**Side effects:**

For the purpose of regulatory reporting requirements during clinical development, the following AEs will be considered as expected and met the threshold of casual association (based on comprehensive evaluation) defined by the Sponsor:

- ξ Infusion-related reactions including hypersensitivity reactions
- ξ Immune-mediated adverse reactions like immune-mediated colitis, immune-mediated hepatitis including autoimmune hepatitis, immune-mediated thyroid disorders including hyperthyroidism, hypothyroidism, thyroiditis and autoimmune thyroiditis, immune-mediated pneumonitis, immune-mediated skin reactions including rash, pruritis, rash generalized, rash macula-papular, erythema, pemphigoid, other immune mediated reactions including myocarditis, adrenal insufficiency, uveitis, iritis, myositis.

**Special Precautions for Administration:**

- ξ Setting: Avelumab should be administered in a setting that allows for immediate access to an intensive care unit or equivalent environment and administration of therapy for anaphylaxis, such as the ability to implement immediate resuscitation measures. Steroids (dexamethasone 10 mg), epinephrine (1:1,000 dilution), allergy medications (IV antihistamines), bronchodilators, or equivalents, and oxygen should be available for immediate access.
- ξ Observation period: Following avelumab infusions, patients must be observed for 2 hours post-infusion for potential infusion-related reactions.

**Safety assessments:**

- ξ Blood chemistry and hematology assessments: must be performed at baseline, prior to each avelumab dose, at end of treatment visit and at 30 days post-treatment safety follow-up.
- ξ Urine pregnancy test for women of childbearing potential must be performed at baseline and least every month during treatment.
- ξ Free T4 and TSH must be performed at baseline and at least every 8 weeks during treatment and at end of treatment or 30 days post-treatment safety follow-up (if not performed in the previous 8 weeks).

## **7.2 Study Drug Accountability**

The Principal Investigator and Co-investigators are responsible for ensuring accountability for the investigational agent, including reconciliation of materials and maintenance of drug records.

Dispensing and administration of avelumab will be recorded following institutional practices. An accurate accounting will be available for verification. Accountability records will include

- ξ Confirmation of delivery to the site
- ξ Inventory at the site
- ξ Dispensing for each patient
- ξ Return or alternative disposition of unused study drug

Upon completion or termination of the study, all unused and/or partially used avelumab will be destroyed at each site per institutional policy. It is the Principal Investigators' responsibility to arrange for disposal of all empty containers, provided that procedures for proper disposal have been established according to applicable federal, state, local and institutional guidelines and procedures, and provided that appropriate records of disposal are kept.

## 8. MANAGEMENT ALGORITHMS FOR TOXICITIES

### 8.1 DOSING DELAYS/DOSE DISCONTINUATION

The following ADRs require permanent treatment discontinuation of avelumab:

- Any Grade 4 ADRs require treatment discontinuation with avelumab except for single laboratory values out of normal range that are unlikely related to study treatment as assessed by the Investigator, do not have any clinical correlate, and resolve within 7 days with adequate medical management. Patients who experience grade IV toxicity will continue to be followed until toxicity resolution to Grade  $\leq 1$  or return to baseline.

**Any Grade 2 ADR should be managed as follows:**

- If a Grade 2 ADR resolves to Grade  $\leq 1$  by the last day of the current cycle, treatment may continue.
- If a Grade 2 ADR does not resolve to Grade  $\leq 1$  by the last day of the current cycle, infusions should not be given on the following cycle. If at the end of the following cycle the event has not resolved to Grade 1, the subject should permanently discontinue treatment with avelumab ADR (except for hormone insufficiencies, that can be managed by replacement therapy; for these hormone insufficiencies, up to 2 subsequent doses may be omitted).
- Upon the second occurrence of the same Grade 2 ADR (except for hormone insufficiencies that can be managed by replacement therapy) in the same subject, treatment with avelumab has to be permanently discontinued.
- Infusion-related reactions, hypersensitivity reactions (Grades 1 to 4), and tumor lysis syndrome should be handled according to guidelines provided.

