**Table 2 Management of Immune-Related Adverse Events**

Gastrointestinal irAEs		
Severity of Diarrhea / Colitis (NCI-CTCAE v4.03)	Management	Follow-up
Grade 1 Diarrhea: < 4 stools/day over Baseline Colitis: asymptomatic	Continue avelumab therapy Symptomatic treatment (for example, loperamide)	Close monitoring for worsening symptoms Educate subject to report worsening immediately If worsens: Treat as Grade 2 or 3/4
Grade 2 Diarrhea: 4 to 6 stools per day over Baseline; IV fluids indicated < 24 hours; not interfering with ADL Colitis: abdominal pain; blood in stool	Delay avelumab therapy Symptomatic treatment	If improves to Grade 1: Resume avelumab therapy If persists > 5 to 7 days or recur: 0.5 to 1.0 mg/kg/day methylprednisolone or equivalent When symptoms improve to Grade 1, taper steroids over at least 1 month, consider prophylactic antibiotics for opportunistic infections, and resume avelumab therapy per protocol. If worsens or persists > 3 to 5 days with oral steroids: Treat as Grade 3 to 4
Grade 3 to 4 Diarrhea (Grade 3): ≥ 7 stools per day over Baseline; incontinence; IV fluids ≥ 24 hrs; interfering with ADL Colitis (Grade 3): severe abdominal pain, medical intervention indicated, peritoneal signs Grade 4: life-threatening, perforation	Discontinue avelumab therapy per protocol 1.0 to 2.0 mg/kg/day methylprednisolone IV or equivalent Add prophylactic antibiotics for opportunistic infections Consider lower endoscopy	If improves: Continue steroids until Grade 1, then taper over at least 1 month If persists > 3 to 5 days, or recurs after improvement: Add infliximab 5 mg/kg (if no contraindication), Note: Infliximab should not be used in cases of perforation or sepsis

Dermatological irAEs		
Grade of Rash (NCI-CTCAE v4)	Management	Follow-up
Grade 1 to 2 Covering ≤ 30% body surface area	Symptomatic therapy (for example, antihistamines, topical steroids) Continue avelumab therapy	If persists > 1 to 2 weeks or recurs: Consider skin biopsy Delay avelumab therapy Consider 0.5 to 1.0 mg/kg/day methylprednisolone IV or oral equivalent. Once improving, taper steroids over at least 1 month, consider prophylactic antibiotics for opportunistic infections, and resume avelumab therapy If worsens: Treat as Grade 3 to 4

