Grade 3 to 4 Covering > 30% body surface area; life threatening consequences	Delay or discontinue avelumab therapy Consider skin biopsy Dermatology consult 1.0 to 2.0 mg/kg/day methylprednisolone IV or IV equivalent	If improves to Grade 1: Taper steroids over at least 1 month and add prophylactic antibiotics for opportunistic infections Resume avelumab therapy
Pulmonary irAEs		
Grade of Pneumonitis (NCI-CTCAE v4)	Management	Follow-up
Grade 1 Radiographic changes only	Consider delay of avelumab therapy Monitor for symptoms every 2 to 3 days Consider Pulmonary and Infectious Disease consults	Re-image at least every 3 weeks If worsens: Treat as Grade 2 or Grade 3 to 4
Grade 2 Mild to moderate new symptoms	Delay avelumab therapy Pulmonary and Infectious Disease consults Monitor symptoms daily, consider hospitalization 1.0 mg/kg/day methylprednisolone IV or oral equivalent Consider bronchoscopy, lung biopsy	Re-image every 1 to 3 days If improves: When symptoms return to near Baseline, taper steroids over at least 1 month and then resume avelumab therapy and consider prophylactic antibiotics If not improving after 2 weeks or worsening: Treat as Grade 3 to 4
Grade 3 to 4 Severe new symptoms; New / worsening hypoxia; life-threatening	Discontinue avelumab therapy Hospitalize Pulmonary and Infectious Disease consults	If improves to Baseline: Taper steroids over at least 6 weeks If not improving after 48 hours or worsening:

	2 to 4 mg/kg/day methylprednisolone IV or IV equivalent Add prophylactic antibiotics for opportunistic infections Consider bronchoscopy, lung biopsy	Add additional immunosuppression (for example, infliximab, cyclophosphamide, IV immunoglobulin, or mycophenolate mofetil)
Hepatic irAEs		
Grade of Liver Test Elevation (NCI-CTCAE v4)	Management	Follow-up
Grade 1 Grade 1 AST or ALT > ULN to 3.0 x ULN and / or total bilirubin > ULN to 1.5 x ULN	Continue avelumab therapy	Continue liver function monitoring If worsens: Treat as Grade 2 or 3 to 4

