### 15.4 Analysis of Primary Objectives

Phase I: If no more than one-third of the subjects permanently discontinue study medication prior to completing six doses due to treatment related adverse events then this combination will be deemed as tolerable and return to the IRB, DMC, and Sponsor for further evaluation and approval prior to proceeding to the Phase II cohort.

If  $\geq 4$  patients in the Phase I cohort permanently discontinue study medication prior to completing six doses due to treatment related adverse events then we will suspend the study and return the study to the IRB and DSMB committees for further evaluation and recommendations.

Phase II: The primary efficacy analysis will be the relapse free survival (RFS) rate in patients with early Stage NSCLC receiving SBRT combined with concurrent and adjuvant Avelumab compared to SBRT alone historical controls. The analysis population includes all registered subjects who have received SBRT and at least 2 cycles of Avelumab.

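### Section 8.1 and Table 2 conflict on some Grade 2 immune-related events, chiefly a second occurrence, and the protocol does not say which governs

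*Combined protocol and SAP*

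**What the plan says.** **Section 8.1, Grade 2 list.** It applies to any Grade 2 adverse drug reaction.

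- If the reaction falls to Grade 1 or lower "by the last day of the current cycle, treatment may continue".
- If it does not, the next cycle's infusion is withheld. "If at the end of the following cycle the event has not resolved to Grade 1, the subject should permanently discontinue treatment".
- "Upon the second occurrence of the same Grade 2 ADR" "in the same subject, treatment with avelumab has to be permanently discontinued". Hormone insufficiencies managed by replacement are excepted from the last two rules.
- Only three kinds of event are referred elsewhere: "Infusion-related reactions, hypersensitivity reactions (Grades 1 to 4), and tumor lysis syndrome should be handled according to guidelines provided". Immune-related events are not among them.

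**Section 8.2, Immune-Related Adverse Events.** Treatment of these events is to follow Table 2. Its rows include:

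- Rash, Grade 1 to 2: continue avelumab at first. "If persists > 1 to 2 weeks or recurs: Consider skin biopsy Delay avelumab therapy"; then consider steroids, taper once the rash is improving, and resume avelumab.
- Diarrhea/colitis, Grade 2: if it persists or recurs, give steroids, taper over at least 1 month, and resume avelumab per protocol.
- Pneumonitis, Grade 2: delay avelumab and give steroids. Once symptoms are near baseline, "taper steroids over at least 1 month and then resume avelumab therapy and consider prophylactic antibiotics".

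**Section 15.4, Phase I.** The decision counts patients who "permanently discontinue study medication prior to completing six doses due to treatment related adverse events". Section 15.2 sets the cohort at 12.

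**The concern.** Both passages claim the same events. Section 8.1 takes in all Grade 2 reactions and does not release immune-related ones; section 8.2 hands immune-related ones to Table 2. Neither says that it yields to the other. Neither is uniformly the stricter, so a site cannot infer a rule of following the more cautious page.

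Two things are at stake. The first is uniform safety conduct and exposure: two sites could handle the same patient differently and each point to the protocol. The second is the Phase I decision. Whether a patient is permanently stopped is exactly what section 15.4 counts, and for a repeated Grade 2 event the answer depends on which passage was followed.

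**Working it through.** **1. Second occurrence of the same Grade 2 event**

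| Event | Section 8.1 | Table 2 | Can both be followed? |
|---|---|---|---|
| Grade 2 rash returns at Grade 2 | Permanent stop | Delay, then resume | No |
| Grade 2 colitis returns at Grade 2 | Permanent stop | Steroids, taper, resume per protocol | Only if that phrase points back to 8.1 |

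**2. Grade 2 pneumonitis that settles within the cycle**

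Inputs: 14-day cycles and six doses (section 6.3.1); a taper of at least 1 month (Table 2).

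Schedule check: 6 x 14 = 84 days, or 84 / 30.44 = 2.8 months. This agrees with the approximately 3 months in section 6.5. The infusion days are 1, 15, 29, 43, 57 and 71.

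Suppose that the event occurs and settles in cycle 1 and the taper starts that day.

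- Section 8.1: the day 15 dose is permitted, so 0 doses are held.
- Table 2: with settling on days 2 to 14 and a month of 28 to 31 days, restart is possible at the earliest on day 2 + 28 = 30 and at the latest on day 14 + 31 = 45. The day 15 and day 29 doses are always passed. The day 43 dose is also passed if restart falls on day 44 or 45.
- Result: 2 to 3 of 6 scheduled doses (33% to 50%) for a taper of the minimum length.

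The figure of at least 2 needs two doses still to come, so it holds for events in cycles 1 to 4. The documents do not say whether held doses are lost or given later. Table 2 speaks of delay. Section 8.1 speaks of infusions not being given, and of omission only for hormone insufficiencies.

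Neither passage orders a permanent stop in this case, so it adds nothing to the 15.4 count.

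**3. Bearing of the recurrence conflict on section 15.4**

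The suspension threshold is 4 of 12. The documents give no rate for repeated Grade 2 events or for discontinuation, so the following is an illustration on assumed rates and not a forecast. Let one patient have a repeated Grade 2 event, and let each of the other 11 discontinue independently with probability p.

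- If that patient resumes and completes treatment, suspension needs 4 or more of the other 11: P(Bin(11, p) ≥ 4).
- If that patient is stopped, it needs 3 or more of the other 11: P(Bin(11, p) ≥ 3).

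| Assumed p | Patient resumes (Table 2) | Patient stopped (8.1) |
|---|---|---|
| 10% | 1.9% | 9.0% |
| 15% | 6.9% | 22.1% |
| 20% | 16.1% | 38.3% |
| 25% | 28.7% | 54.5% |

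So if such a patient occurs, the classification matters. How often one would occur is not known.

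**4. Related timing differences, on which the point does not rest**

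The Grade 2 hepatic row resumes avelumab after recovery and taper without naming a time limit, whereas 8.1 sets one. Grade 2 pneumonitis not improving after 2 weeks moves to a Table 2 row that discontinues avelumab, whereas 8.1 waits to the end of the following cycle.

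**The case against.** The strongest reply is that the passages can mostly be read together.

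- **Pneumonitis.** Section 8.1 only permits the next dose. A site that holds through the Table 2 taper breaks neither passage, and 8.1's permanent stop is triggered by non-resolution, not by a long hold after resolution. This stands. A reader might infer that the two pages give opposite orders for pneumonitis, or that this case alters the Phase I count. The text supports neither.
- **Colitis.** The reference to the protocol in its resume instruction can fairly be read as bringing back 8.1's second-occurrence stop. This stands as a possible reading; the rash row has no such phrase.
- **Rash.** The row joins Grades 1 and 2, so recurrence there could mean a return at Grade 1, or one episode that comes and goes. That narrows the conflict but does not remove it: the row also covers a return at Grade 2, for which 8.1 requires a stop.
- **Compatible events.** Grade 2 colitis or hepatic events that clear quickly without steroids are handled compatibly. The conflict is therefore not general.

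Two further inferences should be resisted. A reader might take the figure of under 10% in section 12.4 as about one Grade 2 pneumonitis case in 12. That figure is an upper bound for radiation pneumonitis, with no grade given, and is not a rate of Grade 2 immune-related events. A reader might also infer that patients whose doses are withheld escape the Phase I count. Section 15.1.1 assesses tolerability once every patient has either completed six doses or discontinued before that, so the documents do not support a third, uncounted group.

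**Conclusion.** The protocol conflicts with itself for some Grade 2 immune-related events and states no precedence. The conflict is direct for a second occurrence of Grade 2 rash and arguable for colitis. For Grade 2 pneumonitis settling within the cycle, the restart timing is inconsistent by at least 2 of 6 scheduled doses against 0. This assumes that at least two doses remain and that the taper starts when symptoms settle; it affects exposure and safety conduct only.

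The recurrence conflict feeds the section 15.4 count, where the threshold is 4 of 12. Its effect cannot be sized from the documents; the probabilities above depend wholly on assumed rates. The point merits a correction. It does not show that the Phase I rule is invalid, and it takes no position on which clinical instruction is right.

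**What to change.** Reconcile the Grade 2 list in section 8.1 with the Grade 2 rows of Table 2. State in both places which governs Grade 2 immune-related events. The reconciled text should settle:

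- when avelumab may restart, including any limit on the length of a hold;
- what happens on a second occurrence, which grades the rash row's recurrence wording covers, and what the colitis row's reference to the protocol points to;
- whether held doses are omitted or delayed.

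The medical leads decide which rule stands. Section 15.4 can keep its criterion; it needs only a statement that permanent discontinuations are counted according to the reconciled rule.

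The cost is a wording amendment with the IRB approval that section 14.1 requires, plus site retraining. No extra patients or procedures are needed.
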